### 9.5 Qualification/Disqualification Criteria for Clinical Trial Results

The non-inferiority hypothesis is tenable if the lower limit of 95% confidence interval of the difference in the primary effectiveness evaluation indicator "device cutting and anastomosis success rate" between the test group and the control group is greater than the non-inferiority critical value (-10%).

The secondary effectiveness evaluation indicators and safety evaluation indicators are tested by difference test, and the significance level is set at 0.05. If the test result of the difference in any secondary evaluation indicator and safety evaluation indicator between the test group and the control group is p > 0.05, then there is no significant difference in this indicator between the test group and the control group.

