- (5) Parallel positive control: The investigational medical device has the mature application technology with many similar products that are marketed at home and abroad. It has been used in clinical practice for many years, with exact effect and predictable occurrence of adverse events. Therefore, parallel positive control is adopted in this clinical trial.

(6) Non-inferiority test: To evaluate whether the main effectiveness evaluation indicator "success rate of cutting and anastomosis" of the Disposable Powered Articulating Endoscopic Linear Cutter Stapler manufactured by Fengh Company is non-inferior to the similar product manufactured by Johnson & Johnson Company in total-thoracoscopic anatomic lobectomy (segmentectomy). The purpose of the non-inferiority test is to validate that if the effectiveness and safety of the investigational medical device is lower than those of the control device. The difference should be less than the pre-defined non-inferiority margin, that is, the difference should be acceptable in clinical practice.

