## 9.2 Sample Size Calculation

#### 9.2.1 Total sample size

164 subjects are planned to be enrolled in this clinical trial. The sample size determination process is as follows:

This clinical study is a parallel positive control clinical validation design. The "device cutting and anastomosis success rate" is adopted as the basis for sample size estimation. Based on literature review , a

total of 160 patients were included in the study. All patients underwent thoracoscopic surgery with Johnson & JohnsonTM Echelon linear cutter stapler. During the surgery, 8 patients were converted into thoracotomy. Only 1 case of conversion to thoracotomy was resulted from linear cutter stapling failure. The other reasons were: intraoperative pulmonary artery bleeding in 3 cases, pulmonary vein bleeding in 1 case, lymph node metastasis or lymph node calcification and adhesion in 2 cases, and pulmonary artery anatomical malformation in 1 case. Therefore, when the similar device was used for VAT anatomical lobectomy (segmentectomy), the success rate of device cutting and anastomosis was up to 99.38% (1/160). The clinical investigators participating in this trial determined that the "device cutting and anastomosis success rate" of this clinical trial was conservatively estimated to be 97%, with a clinical non-inferiority margin of -10% based on the relevant literatures and considering the clinical practice. The parameters were set as follows:  $\alpha = 0.025$  (one-sided),  $\beta = 0.2$ ,  $\delta = -10\%$ , and the ratio of test group and the control group was 1:1. The formula of sample size estimation for non-inferiority clinical validation is adopted, and the sample size required in each group is at least 65 cases. The calculation formula and correction formula are as follows:

$$n_{3} = \frac{(\pi_{A}(1 - \pi_{A}) + \pi_{B}(1 - \pi_{B}))(Z_{1-\beta} + Z_{1-\alpha})^{2}}{((\pi_{A} - \pi_{B}) - d)^{2}}$$
$$n_{4} = \frac{n_{3} \left\{ 1 + \left[1 + \frac{4}{(\delta n_{3})}\right]^{\frac{1}{2}} \right\}^{2}}{4}$$

Considering that the number of subjects who may drop out or be lost to follow-up during clinical validation is about 20%, the sample size of each group is expanded to 82 cases, and the total sample size required for the two groups is 164 cases.

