#### 9.3 Significance Level and Power of Clinical Trial

Significance level  $\alpha$  (one-sided) = 0.025 with 80% power.

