# 9.7 Statistical Methods of Data, Together with Processing Methods of Missing, Unused or Wrong Data and Unreasonable Data

#### 9.7.1 Statistical method for data

Statistical analysis is performed using the SAS 9.1 software.

Statistical description on all data, including demographic data, baseline data, all efficacy indicators and all safety data shall be performed. Measurement data will be statistically described using mean, standard deviation, minimum, maximum, median, 25th percentile and 75th percentile; enumeration data will be statistically described using frequency and percentage.

The primary effectiveness evaluation indicator (device cutting and anastomosis success rate) is evaluated by the confidence interval method.

The secondary evaluation indicators are evaluated by the difference test. Measurement data are compared using two independent samples t-test. Enumeration data are compared using Pearson's  $X^2$  test or Fisher's

exact test.

The safety evaluation indicators are evaluated by the difference test. Measurement data are compared using two independent samples t-test. Enumeration data are compared using Pearson's  $X^2$  test or Fisher's exact test. The adverse events and device defects occur in this trial shall be shown in list.

The stapler operational performance is evaluated by the difference test, with the Pearson's  $X^2$  test or Fisher's exact test.

The central effect is considered in the analysis process. The general linear model is used for measurement data, and CMH is used for enumeration data.

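### Safety and secondary indicators are compared only by a 0.05 difference test, with no interval or margin, although section 8.1.3(6) says safety is validated within a margin; p > 0.05 at 82 per arm is weak evidence of comparable safety.

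*Combined protocol and SAP*

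**What the plan says.** Section 9.5 has two parts. The first is the success rule for the primary indicator: the lower 95% confidence limit for the difference in success rate must lie above -10%. The second covers the secondary effectiveness and safety indicators. They are tested for a difference at the 0.05 level, and when p exceeds 0.05, "then there is no significant difference in this indicator between the test group and the control group". No consequence is attached to either outcome of these tests.

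Section 9.7.1 uses the confidence interval method for the primary indicator only. For safety, "The safety evaluation indicators are evaluated by the difference test", by t test for measurements and by Pearson chi-square or Fisher's exact test for counts. It gives no rule for choosing between the last two. Centre effect is handled with a general linear model or CMH, with no estimate or interval specified.

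Section 8.1.2 frames the secondary and safety objectives as whether there are differences. Section 8.1.3(6) begins with the primary indicator but then widens the scope: "The purpose of the non-inferiority test is to validate that if the effectiveness and safety of the investigational medical device is lower" than the control's, the difference should be smaller than a pre-defined margin.

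Section 9.2.1 sets the only margin in the document, for the cutting and anastomosis success rate, and sizes the trial on that endpoint alone. No safety indicator has an expected rate, a margin or a power statement.

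**The concern.** The trial's stated purpose (abstract and section 3.1) is to compare effectiveness and safety in support of a registration application, so safety is part of the conclusion. The plan's only between-group statement on safety would be whether p exceeded 0.05.

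A difference test that fails to reject does not show similarity. It may only show that the sample was too small to tell. The incentive also runs the wrong way, because fewer subjects or noisier data make the reassuring label easier to obtain. Section 8.1.3(6) meanwhile invites the reader to think that safety has been shown to lie within a limit, when no such hypothesis is defined or analysed.

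**Working it through.** **1. What the sample size was built for.** Inputs from section 9.2.1: 97% success in both arms, margin 10 points, one-sided alpha 0.025, power 80%, and "the ratio of test group and the control group was 1:1".

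- n3 = 2 × 0.97 × 0.03 × (0.842 + 1.960)² / 0.10² = 45.7, rounded up to 46.
- The protocol's correction: n4 = 46 × {1 + [1 + 4/(0.10 × 46)]^½}² / 4 = 64.4, rounded up to 65. This agrees with "the sample size required in each group is at least 65 cases".
- 65 / 0.80 = 81.25, rounded up to 82, which agrees with "the sample size of each group is expanded to 82 cases"; 2 × 82 = 164.

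The stated figures reproduce. No safety rate enters the calculation.

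**2. How often a real excess gives p > 0.05.** The documents give no expected safety rates, so the rates below are assumptions, shown over a range. The test is taken as two-sided at 0.05, since section 9.5 does not state sidedness. With X events in the control arm and Y in the test arm, each binomial with n = 82, the chance is the sum of P(X = a) × P(Y = b) over all pairs (a, b) whose p-value exceeds 0.05. Both tests are shown because the choice is left open.

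| Control v test rate | Fisher, chance of p > 0.05 | Pearson, chance of p > 0.05 |
|---|---|---|
| 2% v 6% | 88% | 77% |
| 5% v 10% | 85% | 78% |
| 10% v 20% | 64% | 57% |
| 15% v 30% | 43% | 36% |
| 2% v 12% | 36% | 26% |
| 20% v 40% | 24% | 19% |

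These figures are for one indicator counted per subject. They do not apply to the device-defect rate, which section 8.1.8(7) defines per device.

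**3. Effect of fewer subjects.** Using Fisher when an expected count is below 5 and Pearson otherwise, the chance of p > 0.05 for 5% v 10% is 80% at 82 per arm and 84% at 65 per arm.

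**4. What the label can hide.** Suppose 4/82 control and 11/82 test subjects have an event (4.9% v 13.4%).

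- Pearson: chi-square = 164 × (4 × 71 − 11 × 78)² / (82 × 82 × 15 × 149) = 3.60, p = 0.058. Fisher: p = 0.10.
- Under section 9.5 either result reads as no significant difference.
- Newcombe 95% interval. The Wilson limits are 7.7% to 22.4% (test) and 1.9% to 11.9% (control), and the difference is 0.0854. Lower limit: 0.0854 − √[(0.1341 − 0.0766)² + (0.1188 − 0.0488)²] = −0.005. Upper limit: 0.0854 + √[(0.2245 − 0.1341)² + (0.0488 − 0.0191)²] = 0.180.

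The data would be compatible with an excess of up to 18.0 points, and the planned output would not show it.

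**5. Sections side by side.** Section 8.1.3(6) speaks of safety within a pre-defined margin. Sections 8.1.1, 9.2.1 and 9.5 apply non-inferiority and the -10% margin to the primary success rate only. Sections 8.1.2 and 9.7.1 treat safety as a question of difference. The safety wording in 8.1.3(6) has no matching hypothesis or analysis.

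**The case against.** The best defence is that section 9.5 contains one explicit success criterion, the primary one, and that the safety sentence merely names a test result. That stands. A reader might infer from the section heading that p > 0.05 is a pass rule for every indicator, but the text attaches no qualifying or disqualifying consequence to either outcome.

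The safety objective in 8.1.2 does match the difference tests in 9.7.1, and the mention of safety in 8.1.3(6) may be loose wording in a translated text. That is a reason for a simple correction, but the contradiction remains until it is made.

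Safety is also not judged on p-values alone. Section 9.7.1 requires frequencies and percentages and a listing of adverse events and device defects. Section 9.7.2 imputes missing safety values by the worst case and adds a sensitivity analysis. A reader could compute intervals from the counts. This softens the point without removing it, because the only planned between-group inference is still the test. Section 9.1 defers detail to a statistical analysis plan that could add intervals, but no such provision appears in the text reviewed.

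Two stronger readings are not supported:

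- **A clearly less safe device would usually escape notice.** This depends on rates the documents do not give, and it fails for larger differences, as the last three rows of the table show. A device worse on several indicators would also be flagged more often than the single-indicator figures suggest.
- **Twelve unadjusted tests would mark down an identical device up to 46% of the time** (1 − 0.95^12). This needs twelve independent, exact 5% tests. Fisher's actual size at 82 per arm is about 0.3% to 2.9% for event rates of 2% to 10%. The indicators overlap, since section 8.1.8(5) counts staple-line events as serious adverse events. Nor does section 9.5 state any penalty for p below 0.05.

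**Conclusion.** The point holds in a limited form. The plan's only between-group comparison of secondary and safety indicators is a difference test, with no interval or margin, and section 8.1.3(6) claims more for safety than any analysis delivers. At 82 per arm, a rise from 2% to 6%, or a doubling from 5% or 10%, would more often than not give p > 0.05 on a single indicator (57% to 88%, depending on rates and test). Larger differences would usually be detected. The size rests on assumed event rates, full arms of 82, two-sided tests and one indicator at a time.

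The primary analysis and the sample size are unaffected. What changes is what the trial can properly say about safety. It should be fixed, and it is a cheap improvement.

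**What to change.** - **Sections 9.5 and 9.7.1:** for each secondary and safety indicator, report test minus control with a two-sided 95% confidence interval (for example Newcombe for proportions of subjects, and the mean difference for times and stitch counts). Present the p-values as descriptive. State that p > 0.05 is not evidence of similar safety, and that safety conclusions will be worded from the interval limits, as the excess that the data exclude.
- **Section 8.1.3(6):** limit the non-inferiority claim to the primary effectiveness indicator.
- **Timing:** write the intervals into the statistical analysis plan before database lock (section 9.1), because section 9.8 treats later additions as exploratory.

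The cost is wording in three sections and one extra table column, with no additional subjects or data. The downside is that safety statements will read less favourably.

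Keeping a safety non-inferiority claim instead would require a justified margin and its own sample size. As an illustration only, take a 10-point margin, equal true rates, one-sided alpha 0.025 and 80% power. Then n = 2p(1 − p) × 7.849 / 0.10², which is 75 per arm at a 5% event rate and 142 at 10%. With these assumptions, 82 per arm would be enough only for low rates.

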#### 9.6 Criteria and Reasons for Terminating Trial Based on Statistical Reasons

No interim analysis will be performed for this study, therefore, no standard for terminating the trial for statistical reasons is developed.

# 9.7 Statistical Methods of Data, Together with Processing Methods of Missing, Unused or Wrong Data and Unreasonable Data

#### 9.7.1 Statistical method for data

Statistical analysis is performed using the SAS 9.1 software.

Statistical description on all data, including demographic data, baseline data, all efficacy indicators and all safety data shall be performed. Measurement data will be statistically described using mean, standard deviation, minimum, maximum, median, 25th percentile and 75th percentile; enumeration data will be statistically described using frequency and percentage.

The primary effectiveness evaluation indicator (device cutting and anastomosis success rate) is evaluated by the confidence interval method.

The secondary evaluation indicators are evaluated by the difference test. Measurement data are compared using two independent samples t-test. Enumeration data are compared using Pearson's  $X^2$  test or Fisher's

exact test.

The safety evaluation indicators are evaluated by the difference test. Measurement data are compared using two independent samples t-test. Enumeration data are compared using Pearson's  $X^2$  test or Fisher's exact test. The adverse events and device defects occur in this trial shall be shown in list.

The stapler operational performance is evaluated by the difference test, with the Pearson's  $X^2$  test or Fisher's exact test.

The central effect is considered in the analysis process. The general linear model is used for measurement data, and CMH is used for enumeration data.

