#### 8.1.3 Selection of test method and reasons

This clinical trial is a "prospective, multi-center, stratified-block randomization, incomplete blinding, parallel positive control, non-inferiority test".

- (1) Prospective: A research method that tracks from the present to the future. Prospective studies can clarify the causal relationship; uniform diagnostic, detection, and evaluation criteria can be available for the obtained data, the data processing therefore is controllable.
- (2) Multi-center: 5 clinical trial institutions were selected to conduct this clinical trial. The application of multi-center trial can allow to obtain more cases than those of single-center trial in the same time, the clinical trial time therefore can be shortened; since the multi-center trial is completed by different regions, different trial centers and many clinical researchers, the conclusion therefore is often widely representative.
- (3) Stratified block randomization: This trial adopts the stratified block randomization method (with the study site as the stratification factor) and the randomization envelope to randomize the subjects who are screened successfully. The randomized-grouping time is that before the surgery. Randomized grouping ensures that, except for treatment factors, other non-treatment factors that may have confounding effect are kept consistent in each group as far as possible, so as to ensure the balance of baseline of each group; randomized-grouping allows each subject to have equal opportunity to be assigned to the test group or control group.
- (4) Incomplete blinding: Since the investigational medical device and the control medical device are different in appearance, while the subjects are under anesthesia during the operation, the grouping arrangement can not be known. Therefore, the method of incomplete blinding is used, that is, the investigators knows the grouping result, while the subject does not know the grouping result. Blinded data review is also required at the same time. Incomplete blinding can minimize the bias caused by "placebo effect", and make the evaluation of adverse reactions by subjects more objective.

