## 9. Statistical Considerations

#### 9.1 Statistical Design, Methods and Analysis Procedure

This study is a prospective, multi-center, stratified block randomization, incomplete blinding, parallel positive control and non-inferiority test. All statistical analysis methods are detailed in the statistical analysis plan. The first draft of the statistical analysis plan will be formed after the trial protocol and case report forms are finalized and will be finalized before database lock.

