## 9.8 Procedures for Reporting Deviations from Original Statistical Plan

In general, only the statistical analysis contents pre-specified in the statistical analysis plan can be presented in the clinical trial report of this trial. The increased need for statistical analysis due to various indeterminate reasons will be considered exploratory only.

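### Does leaving the confidence-interval method unnamed for the primary non-inferiority comparison put the stated 2.5% error rate at risk?

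*Combined protocol and SAP*

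**What the plan says.** Section 9.5 gives the decision rule. Non-inferiority holds if the "lower limit of 95% confidence interval of the difference in the primary effectiveness evaluation indicator" between test and control exceeds -10%. Sections 9.2.1 and 9.3 set a one-sided significance level of 0.025 and 80% power. Section 9.7.1 adds only that "The primary effectiveness evaluation indicator (device cutting and anastomosis success rate) is evaluated by the confidence interval method". On centre effects it says: "The general linear model is used for measurement data, and CMH is used for enumeration data".

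The detail is deferred. Section 9.1 leaves all methods to a statistical analysis plan whose first draft "will be formed after the trial protocol and case report forms are finalized and will be finalized before database lock". Under Section 9.8, in general, "only the statistical analysis contents pre-specified in the statistical analysis plan can be presented in the clinical trial report of this trial". The text of a separate analysis plan is not part of the document reviewed. On timing and access to results, Section 8.1.3 states: "Blinded data review is also required at the same time". Section 9.6 states: "No interim analysis will be performed for this study".

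Section 9.2.1 introduces its sample size with "The calculation formula and correction formula are as follows". It then gives two formulas, the second of which is a continuity correction of the first.

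**The concern.** The trial turns on one number, yet the method that produces it is described less fully than the tests for the secondary and safety endpoints. Those are named: t-test, Pearson chi-square, Fisher's exact test. Several 95% intervals for a difference of proportions fit the words of Sections 9.5 and 9.7.1. Near 100% success they do not behave alike, and the simplest one, uncorrected Wald, is too short in a direction that favours the new device.

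The reference to CMH does not fill the gap. CMH tests association and gives no limit to compare with -10%, although randomisation is stratified by centre (Section 8.2.3).

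Two things would be at stake: a true error rate above the stated 2.5%, and opposite verdicts from the same data according to which interval the analyst picks. Investigators know the allocation (Sections 8.1.3 and 8.2.4), so an interval chosen late could in principle be chosen with some idea of the results.

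**Working it through.** **Inputs.** Success 97% in both arms, margin 10 percentage points, one-sided alpha 0.025, power 80%, allocation 1:1, at least 65 per group, 82 after loss (Section 9.2.1). Expected loss 20% (Section 9.4). Literature success rate 99.38% (Section 9.2.1).

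**The plan's own sample size.** The margin is taken as the magnitude δ = 0.10.

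- n3 = 2 × 0.97 × 0.03 × (1.960 + 0.842)² / 0.10² = 0.0582 × 7.849 / 0.01 = 45.68.
- n4 = n3 × {1 + √[1 + 4/(δ n3)]}² / 4 = 45.68 × (1 + √1.8757)² / 4 = 64.12, so 65.
- 65 / 0.8 = 81.25, so 82 per group and 164 in total.

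All three stated figures reproduce.

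**What the correction implies.** A continuity-corrected Wald lower limit subtracts a further (1/n + 1/n)/2 = 1/n. With no true difference, its approximate power equation is

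δ − 1/n = (z₁₋α + z₁₋β) × √(2 × 0.97 × 0.03 / n).

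The right side equals δ√(n3/n). Multiplying by n and solving the quadratic in √n gives √n = √n3 × {1 + √[1 + 4/(δ n3)]} / 2, which squared is exactly n4. Check at n = 64.12: the left side is 0.10 − 0.0156 = 0.0844, and the right side is 2.802 × √(0.0582/64.12) = 0.0844. The design formula therefore sizes the trial for the corrected Wald interval.

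**Error and power of four intervals.** With d the observed difference (test minus control), the lower limits are:

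- Wald: d − 1.96 × √[pT(1−pT)/n + pC(1−pC)/n].
- Corrected Wald: the same, minus 1/n.
- Newcombe: d − √[(pT − lT)² + (uC − pC)²], where lT and uC are Wilson limits.
- Miettinen-Nurminen: the difference at which the score statistic, with restricted variance multiplied by 2n/(2n−1), equals 1.96.

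The exact probability of passing is the sum, over all pairs of success counts whose lower limit exceeds -10%, of the product of the two binomial probabilities. Error is taken at a true difference of -10 points, power at 97% in both arms. Entries are for 65 / 82 per arm.

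| Interval | Error, control 97% | Error, control 99.38% | Power at 97% |
|---|---|---|---|
| Wald | 4.08% / 4.25% | 7.6% / 6.2% | 89.7% / 95.1% |
| Corrected Wald | 2.29% / 1.87% | 2.9% / 2.4% | 80.6% / 87.7% |
| Newcombe | 2.25% / 2.14% | 1.6% / 1.5% | 76.8% / 86.1% |
| Miettinen-Nurminen | 1.78% / 2.14% | 1.3% / 1.5% | 71.9% / 86.1% |

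A simulation of 2 million trials gave 4.10% and 4.27% for Wald. At 97% control success the other three stay below 2.5% at every equal group size from 65 to 82.

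**How often the verdict depends on the interval.** With a true 97% in both arms, the four intervals disagree in 17.8% of trials at 65 per arm and 9.2% at 82. Leaving out uncorrected Wald, the figures are 8.7% and 1.9%. At 99.38% in both arms they are 4.4% and 0.9%, or 3.7% and 0.8% without Wald.

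Splits arise mainly when the test arm has a few more failures than control. For 3/82 v 0/82 failures, d = −0.0366 and the standard error is 0.0207. Wald gives −7.7% and corrected Wald −8.9% (pass); Newcombe and Miettinen-Nurminen give −10.2% (fail). Equal counts can split too. At 5 v 5 of 65, Wald gives −1.96 × √(2 × 0.0769 × 0.9231/65) = −9.2% (pass), while subtracting 1/65 gives −10.7% (fail). With 2 v 2 or 2 v 1 failures at either size, all four pass.

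**Centre.** In simulations of 300,000 trials per setting with five centres, stratifying the Miettinen-Nurminen interval changed its verdict in 0.6% to 1.3% of trials at 97%.

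**The case for a change.** The strongest reply is that silence is not a specification. Section 9.2.1 never ties its correction to the analysis, uncorrected Wald fits the words of Section 9.7.1, and it breaks the stated error rate. Even among the other three, 8.7% of trials at 65 per arm would get a different answer. The low end cannot be dismissed. The endpoint is judged during surgery (Section 8.1.7.1), so a full-analysis-set result may sit near 82 per arm. But Section 9.9 also makes the per-protocol set primary for efficacy, and Section 9.4 counts missed follow-up as loss.

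Nor is the implied interval flawless. If control success is 99.38%, corrected Wald has 2.9% error at 65 per arm, and 3.9% at 74.

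All of that stands as fact. It does not show that the plan is wrong. The 4.1% to 4.3% depends on an interval that nothing in the document selects and that the sample-size formula points away from. Replacing the implied interval with a stratified Miettinen-Nurminen interval would be a trade: firmer error control near 100% success, against power of about 72% to 73% at 65 per arm, below the 80% in Section 9.3, and possibly extra programming. Stratification would add almost nothing to the verdict. On timing, completion before lock, blinded data review and the absence of an interim look limit the room for a choice led by results. They do not remove it, because investigators are unblinded.

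**Conclusion.** No change to the plan follows. Effect measure, confidence level, direction and margin are fixed in Section 9.5. What is missing is the construction of the limit, and Sections 9.1 and 9.8 assign that to the analysis plan. An analyst who follows the design formula arrives at the corrected Wald interval, with 2.3% error at 65 per arm and 1.9% at 82 under the planned 97%, and 80.6% power at 65. These agree with the stated 2.5% and 80%. An analyst who prefers Newcombe or Miettinen-Nurminen also holds 2.5% at 97%, at some cost in power if only 65 per arm are evaluable. In either case the protocol's rule works as written.

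The conclusion assumes that the analysis plan names an interval before lock, as Section 9.1 requires, and that it is not uncorrected Wald. Had that interval been prescribed, the excess error of about 1.6 to 1.8 percentage points (4.08 − 2.5 and 4.25 − 2.5) would be a real fault. The error figures assume independent binomial outcomes, equal arms and 97% control success. At 99.38%, corrected Wald exceeds 2.5% at some group sizes, while Newcombe and Miettinen-Nurminen remain below it at 65 and 82 per arm.
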